2.2 Secondary Objectives (Phase II only)

- 2.2.1 To further evaluate the frequency and severity of toxicity.
- 2.2.2 To further evaluate the clinical efficacy of the combination of brentuximab vedotin and rituximab, as measured by PFS and OS at one year after the end of treatment.
- 2.2.3 To evaluate the best response to therapy.
- 2.2.4 To determine the effects of the combination of brentuximab vedotin and rituximab on markers of EBV activation and proliferation.
- 2.2.4 Further evaluate efficacy as measured by time to cytotoxic chemotherapy.
- 2.2.5 Further evaluate efficacy as measured by observed rates of graft rejection.

2.3 Primary Endpoints

- 2.3.1 The primary endpoint for phase I, dose-limiting toxicity (DLT) will be defined as the occurrence of toxicity as detailed in section 4.2 (using CTCAE v 4.03), experienced during the first 3 weeks of study treatment. The MTD, which constitutes the RP2D, will be defined as described in Section 11 (Study Design).
- 2.3.2 The primary endpoint for phase II, response after induction or induction/consolidation, will be defined as the detection of SD, PR, or CR by CT or PET/CT, and/or resolution of marrow-only involvement. CR and PR will each be assessed according to the Revised Response Criteria for Malignant Lymphoma. Assessments will be performed after induction and/or consolidation treatment (if applicable).

2.4 Secondary Endpoints:

- 2.4.1 Adverse events will be defined as those included in CTCAE v 4.03. The occurrence and severity of each will be recorded.
- 2.4.2 PFS will be defined as the time elapsed between treatment initiation and tumor progression or death from any cause (whichever occurs first), with censoring of patients who are lost to follow-up. OS will be defined as freedom from death by any cause.
- 2.4.3 Best response will be assessed by CT or PET/CT according to the Revised Response Criteria for Malignant Lymphoma after induction and/or consolidation (if applicable) and every 12 weeks during maintenance treatment.
- 2.4.4 EBV activation and proliferation will be measured by viral loads as measured at time of enrollment and monthly thereafter in all enrolled patients, until completion of study therapy.
- 2.4.5 Time to initiation of cytotoxic chemotherapy will be defined as the time elapsed between treatment initiation, and time of first non-targeted cytotoxic chemotherapy.
- 2.4.6 Graft rejection will be defined as any of the following: documentation of new or progressive rejection by tissue biopsy of the graft; re-transplantation due to graft rejection; clinical diagnosis of new or progressive graft rejection, since start of treatment on protocol, as given by the patient's transplant physician. Escalation of intensity of immunosuppression will not, by itself, be considered evidence of graft rejection. (Note: patients with clinically active graft rejection will not be excluded from trial enrollment, but will not be considered to have treatment-emergent graft rejection unless progression of rejection is documented.)

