Diagnosis and Main Inclusion Criteria	Adult patients with non-Hodgkin's lymphoma (NHL) related to an immunosuppressed state
Study Product(s), Dose, Route, Regimen	Brentuximab vedotin 1.2 mg/kg IV once weekly for 3 weeks, then 1.8 mg/kg IV once every 3 weeks Rituximab 375 mg/m ² IV once weekly x 4, then once every 6 weeks
Duration of administration	1 year

Statistical Methodology	
Our null hypothesis is that the combination of rituximab and brentuximab vedotin will yield no difference in the ORR as compared to that observed with historical treatments. The historical ORR for both PTLD and EBV-related lymphoma of the elderly, when treated with rituximab (with or without chemotherapy) is estimated at approximately 50% [1, 2]. Therefore, the optimal two-stage design to test the null hypothesis that $P = 0.50$ versus the alternative that $P \geq 0.70$ (the hypothesized ORR to rituximab plus brentuximab vedotin) has an expected sample size of 24. Under these conditions, if the combination is actually not significantly more efficacious, there is a < 0.05 probability (also known as the alpha value) of concluding that it is. If the combination is actually significantly more efficacious, there is a < 0.20 probability (also known as the beta value) of concluding that it is not. Early futility may be declared, such that if 8 or fewer responses are observed among the first 15 patients enrolled, the trial will be stopped and considered no more efficacious than therapy with rituximab alone.

--------------------------------	---

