1.2.1.10 Clinical studies**1.2.1.10.1 Hodgkin's Lymphoma**

The efficacy of brentuximab vedotin in patients with HL who relapsed after ASCT was evaluated in one open-label, single-arm, multicenter trial of 102 patients treated with 1.8 mg/kg of brentuximab vedotin IV over 30 minutes every 3 weeks. An independent review facility performed efficacy evaluations which included overall response rate (ORR = complete remission [CR] + partial remission [PR]) and duration of response as defined by clinical and radiographic measures including computed tomography (CT) and positron-emission tomography (PET) [in accordance with the 2007 Revised Response Criteria for Malignant Lymphoma (modified)]. The 102 patients ranged in age from 15-77 years (median, 31 years) and most were female (53%) and white (87%). Patients had received a median of 5 prior therapies including ASCT.

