As noted above, up-front use of aggressive cytotoxic chemotherapy has been plagued by early TRM and graft rejection, and further clinical experience has suggested that a delayed introduction of aggressive chemotherapy may significantly reduce risks of TRM. For instance, a European cooperative group experience demonstrated the apparent advantage of a rituximab-based risk-stratified sequential treatment (RSST) strategy for PTLD patients [1]. In this model, all patients with a new diagnosis of PTLD are treated with 4 doses of weekly rituximab, followed by re-staging. Those with a complete response (CR) then receive an additional four doses of weekly rituximab, followed by observation, while those with any other response receive four cycles of R-CHOP-21. Among the first 40 patients treated, there was a 93% ORR, with 32% of patients able to avoid cytotoxic chemotherapy, and perhaps most notably, with rates of TRM (1/40 patients) that compare very favorably to historical rates. The potential clinical advantages to limiting exposure to cytotoxic chemotherapy have also been recognized in pediatric PTLD [37]. Also as noted above, most cases of non-transplant autoimmune-related lymphoma are indolent histology [19]. There is little or no data to establish R-CHOP as frontline therapy for such patients, and anthracycline is potentially “over-treatment” for indolent lymphomas in non-immunocompromised hosts [38].

We therefore hypothesize that brentuximab vedotin and rituximab, used together for the upfront treatment of EBV-related lymphoid malignancies, would optimize efficacy as compared to historical controls by A) improving response rates as compared to single-agent rituximab; B) reducing exposure to cytotoxic therapy, and thereby reduce rates of TRM; and C) ultimately improving PFS and OS. We propose a RSST strategy, similar to that described above, such that those patients failing to achieve a PR or CR to combined brentuximab vedotin and Rituximab therapy can then be treated with cytotoxic chemotherapy, with or without additional mAb therapy. Whereas we predict that EBV positivity may predict for response to anti-CD30 therapy, and that targeting of CD20 will serve to effectively deplete the EBV reservoir, tumor samples need express neither in order to enroll.

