4.0 TREATMENT PLAN

Patients will be treated with combination treatment consisting of brentuximab vedotin and rituximab infusions as detailed below. All patients will receive Induction treatment, and those who achieve response (PR or CR) may have an optional cycle of Consolidation treatment, identical to Induction. Maintenance will then continue for up to one year from the first dose of study treatment.

[figure not shown]

TABLE 1: Dosing Summary

	Induction (1 cycle = 4 weeks)	Consolidation* (1 cycle = 4 weeks)	Maintenance (1 cycle = 3 weeks)
Brentuximab Vedotin dosing	1.2 mg/kg IV over 30 mins Weekly x3	1.2 mg/kg IV over 30 mins Weekly x3	1.8 mg/kg IV over 30 mins Once every 3 weeks
Rituximab dosing	375 mg/m ² IV weekly x4	375 mg/m ² IV weekly x4	375 mg/m ² IV once every 6 weeks

*Optional for patients who achieve PR/CR during induction. See section 4.1.3 for stipulations regarding SD.

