4.1.1.1 Brentuximab vedotin

Induction: 1.2 mg/kg IV infusion over 30 minutes, weekly x 3 (1 cycle = 4 weeks; no brentuximab vedotin is given during the fourth week)

Consolidation (optional): Identical to Induction. Those patients who achieve response (PR or CR) after the Induction course may receive an additional treatment of the same (termed Consolidation). In addition, any patients achieving CR to induction, in whom avoidance of Maintenance therapy is sought, can receive consolidation as their final planned therapy. See section 4.1.3 for stipulations regarding stable disease.

Maintenance: 1.8 mg/kg IV infusion over 30 minutes once every 3 weeks (1 cycle = 3 weeks), for a total of one year from the first induction dose or until progression of disease.

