7.5 Stopping Rules

As noted in Section 5.0, the study will be terminated in the event that $\geq 2/3$ patients experience toxicity in cohort -1 (1.2 mg/kg brentuximab vedotin) during Phase I. Likewise, the study will be stopped after the first stage of Phase II if, among the first 15 patients treated, four or fewer patients have a CR or PR, as this will be considered evidence of inadequate efficacy. In addition, the Data Safety Monitoring Committee will monitor the study in accordance with the DSMP and may suspend or close the study to accrual at any point if required, as outlined in the DSMP.

8.0 DRUG INFORMATION**8.1 Brentixumab vedotin**8.1.1 **Other names for the drug(s):** ADCETRIS®**8.1.2 Classification – type of agent**

Antibody-drug conjugate; the antibody is a chimeric IgG1 directed against CD30 and the small molecule, MMAE, is a microtubule disrupting agent.

8.1.3 **Mode of action** The ADC binds to CD30-expressing cells, followed by internalization of the ADC-CD30 complex, and the release of MMAE via proteolytic cleavage. Binding of MMAE to tubulin disrupts the microtubule network within the cell, subsequently inducing cell cycle arrest and apoptotic death of the cells.

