10.1.2 Phase II

Our null hypothesis is that the combination of rituximab and brentuximab vedotin will yield no difference in the rate of ORR as compared to that observed with historical treatments. The historical ORR for both PTLD and EBV-related

lymphoma of the elderly, when treated with rituximab (with or without chemotherapy is estimated at approximately 50% [1, 2]. Therefore, the optimal two-stage design to test the null hypothesis that $P=0.50$ versus the alternative that $P>=0.70$ (the hypothesized ORR to rituximab plus brentuximab vedotin) has an expected sample size of 24. Under these conditions, if the combination is actually not significantly more efficacious, there is a <0.05 probability (also known as the alpha value) of concluding that it is. If the combination is actually significantly more efficacious, there is a <0.20 probability (also known as the beta value) of concluding that it is not. Early futility may be declared, such that if eight or fewer responses are observed among the first 15 patients enrolled, the trial will be stopped and considered no more efficacious than therapy with rituximab alone.

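### The Phase II primary endpoint in Section 2.3.2 counts stable disease as response, but the hypothesis test and its 50% benchmark are for ORR (CR or PR)

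*Combined protocol and SAP*

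**What the plan says.** Section 2.3.2 is the only place that defines the Phase II primary endpoint: "response after induction or induction/consolidation, will be defined as the detection of SD, PR, or CR by CT or PET/CT", and/or clearing of marrow-only disease.

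Section 10.1.2 sets the null hypothesis that the combination will "yield no difference in the rate of ORR as compared to that observed with historical treatments". The Study Summary gives the same design. Both take P = 0.50 from a historical ORR and P ≥ 0.70 as the hypothesised ORR. They state alpha below 0.05, beta below 0.20, an expected sample size of 24, and stopping at eight or fewer responses in the first 15 patients. Neither says which categories count as a response, and neither gives the final success boundary.

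Elsewhere response means CR or PR:
- Section 1.2.1.10.1 expands ORR as CR plus PR.
- Section 1.3 separates out "those patients failing to achieve a PR or CR to combined brentuximab vedotin and Rituximab therapy".
- Section 4.0: "those who achieve response (PR or CR) may have an optional cycle of Consolidation treatment". Section 4.1.1.1 uses the same meaning: "Those patients who achieve response (PR or CR) after the Induction course".
- Section 6.2.3.1 starts duration of response at CR or PR.
- Section 7.5 stops Phase II after the first 15 patients if "four or fewer patients have a CR or PR".
- Section 9.2.2 contrasts CR/PR with SD/PD, which puts SD among the non-responders.

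**The concern.** In a single-arm trial the conclusion rests on what counts as a success and on whether the historical rate counts the same thing. Here the defined endpoint includes SD and the benchmark appears not to. Section 6.2.2.1.5 describes SD as failing to reach CR or PR without progression, and Section 4.1.3 takes SD patients off treatment after the first re-staging unless the investigator chooses Consolidation. Under 2.3.2 a patient taken off in this way is still a primary-endpoint success.

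If 2.3.2 governs, a regimen with no better CR+PR rate than history can pass because of its SD patients, and the reported rate cannot be compared with 50%. If 10.1.2 governs, the endpoint labelled primary is never tested. With both definitions on file, nothing prevents the choice from being made after the data are seen.

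**Working it through.** **Inputs from Section 10.1.2 and the Study Summary:** p0 = 0.50, p1 = 0.70, alpha < 0.05, beta < 0.20, stop if ≤ 8 of 15, expected N = 24. Section 10.2 plans 24 Phase II patients.

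**Assumptions, because the documents do not give them:** an SD rate s of 5%, 10% or 20%; a true CR+PR rate equal to the null, 0.50; and a final cut-off c.

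**Step 1: reproduce the stated design.** With a continue-rule of at least 9 of 15, the probability of declaring success is

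P(success) = Σ (x = 9 to 15) Bin(x; 15, p) × P[Bin(n − 15, p) ≥ c − x].

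An exhaustive search for the optimal two-stage design with these inputs gives 8/15 then 26/43, so success needs c = 27 of 43.
- Alpha at p = 0.50: 0.0499.
- Power at p = 0.70: 0.804.
- Early stopping under the null: P[Bin(15, 0.50) ≤ 8] = 0.696.
- Expected N under the null: 15 + 28 × (1 − 0.696) = 23.5, in line with the stated 24.

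The maximum of 43 is not in the documents; it is what their inputs imply. If the trial ends at 24, the lowest cut-off that holds alpha below 0.05 is 17 of 24 (alpha 0.032, power 0.561); 16 of 24 gives 0.072. Both versions are carried forward.

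**Step 2: let SD count as success while CR+PR stays at 0.50.**

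(a) SD counts at the look and at the end. Put p = 0.50 + s into the formula above. Early stopping is P[Bin(15, 0.50 + s) ≤ 8].

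(b) The look counts only CR/PR and SD is added at the end. X ~ Bin(15, 0.50), continuing if X ≥ 9; Y given X ~ Bin(15 − X, s/0.50); Z ~ Bin(n − 15, 0.50 + s). Success if X + Y + Z ≥ c. Early stopping stays at 0.696.

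| SD rate | (a) ≥17/24 | (a) ≥27/43 | (a) early stopping | (b) ≥17/24 | (b) ≥27/43 |
|---|---|---|---|---|---|
| 0% | 0.032 | 0.050 | 0.696 | 0.032 | 0.050 |
| 5% | 0.085 | 0.155 | 0.548 | 0.074 | 0.118 |
| 10% | 0.190 | 0.349 | 0.390 | 0.133 | 0.198 |
| 20% | 0.561 | 0.804 | 0.131 | 0.247 | 0.292 |

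At 20% SD under (a), the false-success probability equals the design's power, because 0.50 + 0.20 = 0.70.

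(c) As (b), but with the look in Section 7.5 (stop at four or fewer CR/PR). At N = 24 the results are 0.086, 0.192 and 0.554. N = 43 is not tabulated for (c), because that look alone lifts the rate to 0.063 with no SD.

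**Step 3: SD rate at which alpha reaches 0.05.** For ≥17/24 with the 8/15 look, it is 2.2% under (a) and 2.5% under (b). For ≥27/43, almost any non-zero SD rate is enough, since the design starts at 0.0499.

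**The case against.** The best counter-reading is that the test was always on CR+PR. Section 10.1.2 states the null, the benchmark and the target as ORR; Section 7.5 counts CR or PR at the same 15-patient look; and the sentence after the definition in 2.3.2 describes only how CR and PR are assessed. SD in 2.3.2 may be a drafting slip. On that reading alpha is not inflated, and scenario (a), which gives the largest figures in the table, does not arise. This is plausible, but it concedes that the only definition of the primary endpoint is wrong and must be corrected.

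Two further limits stand. First, the make-up of the 50% cannot be checked. ORR is expanded only in background text on another trial, and Section 1.3 reports a 93% ORR, after sequential treatment, for one of the two sources cited for the 50%. If the 50% already included SD, the stated alpha would hold. Second, the SD rates and final cut-offs are assumptions. At 24 patients with 17 or more needed, alpha stays below 0.05 while SD is under about 2.2% to 2.5%.

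The sections on treatment routing (1.3, 4.0, 4.1.1.1) show usage rather than analysis rules. The conflict does not depend on them: 2.3.2 against 7.5, 9.2.2 and 10.1.2 is enough.

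**Conclusion.** The concern holds. The contradiction is in the current text, needs no assumption, and is not reconciled elsewhere in the protocol. It should be fixed before the primary analysis.

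The effect on alpha is conditional on three things: 2.3.2 governs the test, the 50% null is a CR+PR rate, and some patients have SD. The direction is then certain and the size depends on the SD rate. For SD between 5% and 20%, false success with the 8/15 look runs from 0.074 to 0.561 under the 24-patient rule and from 0.118 to 0.804 under the reconstructed 43-patient design. The lower ends apply when SD is added only at the final test. If the test is on CR+PR, there is no inflation and the defect is that the defined primary endpoint is not the one tested.

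**What to change.** Amend Section 2.3.2 by deleting SD, so that response is CR or PR on CT or PET/CT, with the marrow-only clause and the assessment times kept as they are. Add to Section 10.1.2, and to the matching Study Summary text, that a response is a CR or PR at both the 15-patient look and the final test. Report the SD rate separately and descriptively.

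If an endpoint that includes SD is really intended, keep 2.3.2 but re-derive the null, the target and both boundaries from a cited historical CR+PR+SD rate.

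The cost of the first option is a wording amendment with IRB approval under Section 11.7. It needs no extra patients or data. The reported primary rate will be lower than under 2.3.2 if any patient has SD. The disagreement between eight (10.1.2) and four (7.5) responses at the look is a separate matter that this change does not settle; those sections must be reconciled as well.

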3.1 Inclusion Criteria

- 3.1.1 Patients must have a histologically confirmed CD20+ lymphoproliferative disease that is related to an immunosuppressed state (e.g., PTLD, DLBCL of the elderly, iatrogenic immunodeficiency-associated LPD) and for which rituximab monotherapy would be considered to be appropriate frontline therapy.
- 3.1.2 In cases of lymphoproliferative disease arising in patients who are pharmacologically immunosuppressed, reduction of immunosuppression (RI) must be attempted prior to or in conjunction with enrollment, with the exception of those for whom RI would pose excessive threat of clinically significant graft rejection (as judged by local investigator).

NOTE: Patients who are otherwise immunosuppressed (for reasons such as immune dysregulation related to autoimmune conditions, in the absence of pharmacological immunosuppression) may be eligible if, in the opinion of the treating investigator, the risk of immediate treatment with R-CHOP outweighs the benefit for these patients.

- 3.1.3 Patients must have bi-dimensionally measurable disease (at least 1 cm).
- NOTE: Patients with fully resected disease are eligible, and will be evaluable for all toxicity and efficacy endpoints except objective response.*
- 3.1.4 Patients must be ≥ 18 years of age.
- 3.1.5 Patients must have an ECOG performance status ≤ 2 .
- 3.1.6 Patients must have adequate organ and marrow function as defined below (documented within 28 days of registration):
 - absolute neutrophil count $\geq 750/\text{mcL}$
 - platelets $\geq 50,000/\text{mcL}$
 - total bilirubin $\leq 2 \times$ institutional upper limit of normal (ULN)
 - AST(SGOT)/ALT(SPGT) $\leq 3 \times$ institutional ULN
 - creatinine $\leq 2 \times$ institutional ULN

NOTE: Patients who do not meet the above criteria because of disease involvement of the organ in question, or because of acute systemic illness due to lymphoma, may enroll with permission of the study PI and approval from the Data Monitoring Committee. We propose that this flexibility be allowed due to

the heterogeneity of the patient population, the wide range of complications seen in the initial presentation of EBV-related malignancy, and the frequent difficulty encountered in attempting to clearly document that organ dysfunction is the result of an underlying lymphoproliferative disorder.

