4.6 Duration of Therapy

In the absence of treatment delays due to adverse events, treatment may continue for one year or until:

- 4.6.1 Disease progression
- 4.6.2 Inter-current illness that prevents further administration of treatment
- 4.6.3 Unacceptable adverse event(s)
- 4.6.4 Patient decides to withdraw from the study, OR
- 4.6.5 General or specific changes in the patient's condition render the patient unacceptable for further treatment in the judgment of the investigator.

Please also refer to Section 4.8 for additional information regarding off-treatment and off-study criteria.

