4.7 Duration of Follow Up

Once patients are off treatment (whether treatment is completed or they are withdrawn for any reason) patients will be followed with at least one clinic visit every three months, for up to one year from discontinuation of treatment, then every six months up to 3 years from discontinuation of treatment, or until death, whichever occurs first. Patients removed from treatment for unacceptable adverse events will be followed until resolution or stabilization of the adverse event.

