4.8 Removal of Subjects from Treatment and/or Study

Patients can be removed from the study treatment and/or study at any time at their own request, or they may be withdrawn at the discretion of the investigator for safety, behavioral, or administrative reasons. The reason(s) for discontinuation must be documented and may include:

- 5.5.1 Patient voluntarily withdraws from treatment (follow-up permitted);
- 5.5.2 Patient withdraws consent (termination of treatment and follow-up);
- 5.5.3 Patient is unable to comply with protocol requirements;
- 5.5.4 Patient demonstrates disease progression (unless continued treatment with study drug is deemed appropriate at the discretion of the investigator);
- 5.5.5 Patient experiences toxicity that makes continuation in the protocol unsafe;
- 5.5.6 Treating physician judges continuation on the study would not be in the patient's best interest;
- 5.5.7 Patient becomes pregnant (pregnancy to be reported along same timelines as a serious adverse event);
- 5.5.8 Development of second malignancy (except for basal cell carcinoma or squamous cell carcinoma of the skin) that requires treatment, which would interfere with this study;
- 5.5.9 Patient is lost to follow-up. If a research subject cannot be located to document survival during the follow-up period (up to 3 year after starting study treatment), the subject may be considered "lost to follow-up." All attempts to contact the subject during the follow-up period must be documented and approved by the Data Monitoring Committee.

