6.2.1.3 Evaluable for Other Endpoints

- Time to cytotoxic chemotherapy will be evaluated in all patients who receive at least one dose of study treatment.
- Effect on EBV markers will be evaluated in all patients who receive at least one dose of study treatment and have an evaluable TMA collected at baseline.
- Rates of graft rejection will be evaluated in all patients who receive at least one dose of study treatment

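### Graft rejection has no closing time point, no estimator and a denominator that includes patients without a graft, so its rate will reflect follow-up, deaths and later chemotherapy as well as the regimen

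*Combined protocol and SAP*

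**What the plan says.** - **Objective (2.2.5).** "Further evaluate efficacy as measured by observed rates of graft rejection".
- **Definition (2.4.6).** Rejection is met by graft biopsy, by re-transplantation for rejection, or by "clinical diagnosis of new or progressive graft rejection, since start of treatment on protocol, as given by the patient's transplant physician". The time wording sits on the third criterion and gives only a start. The section has two safeguards: rejection already active at entry counts only if progression is documented, and stepping up immunosuppression does not count by itself.
- **Population (6.2.1.3).** "Rates of graft rejection will be evaluated in all patients who receive at least one dose of study treatment".
- **Observation time.** Under 4.6, "treatment may continue for one year or until" progression or another listed reason. Under 4.7, visits then continue "for up to one year from discontinuation of treatment, then every six months up to 3 years from discontinuation of treatment, or until death". Section 4.8 describes a different limit, in the context of attempts to "document survival during the follow-up period (up to 3 year after starting study treatment". Neither limit is tied to graft rejection.
- **Later treatment (4.1.3).** Patients with PD at first re-staging leave protocol treatment for R-CHOP or similar. Patients with SD do the same unless the investigator opts for Consolidation.
- **Reduction of immunosuppression, RI (3.1.2).** It must be attempted in pharmacologically immunosuppressed patients, "with the exception of those for whom RI would pose excessive threat of clinically significant graft rejection".
- **Analysis (Section 10).** It covers the Phase I dose rule, the Phase II ORR test and accrual. It says nothing on graft rejection.

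**The concern.** A rate needs a population at risk, a period at risk, and a rule for patients who leave that period early. For graft rejection the plan states the first in a form that includes people who cannot have the event, and leaves the other two open.

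This endpoint is less fully specified than its neighbours. DLT has a 3-week window, EBV load stops at completion of therapy, PFS counts death and has a censoring rule, and OS is capped at three years from start of treatment (6.2.4).

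The open window also takes in events that follow off-protocol chemotherapy. Sections 1.1 and 1.3 link early cytotoxic chemotherapy to graft rejection, so the regimen's figure may include rejections that followed the exposure the trial hopes to avoid. At stake is whether the reported number can be read at all. The documents give no numeric comparator, so readers will set it against outside figures and need to know its horizon and population.

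**Working it through.** The plan states no rate, precision or sample size for this endpoint, so there is no figure to reproduce. The calculations below show only how far the unspecified choices can move the result.

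**Inputs from the protocol**
- Median OS 2 to 4 years (1.1).
- Treatment up to 1 year (4.6), then up to 3 years off treatment (4.7). The longest observation is 1 + 3 = 4 years.
- A patient who stops at first re-staging, at about 1 month, reaches 1 + 36 = 37 months.
- Phase II enrolment 24 (10.2).

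**Assumptions**
- One-year rejection risk of 15% without competing death, with constant hazards. The documents give no rejection rate.

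**1. Follow-up and death**

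Rejection hazard h = -ln(1 - 0.15) = 0.1625 per year. Death hazard d = ln 2 / median OS = 0.3466 (2 years) or 0.1733 (4 years). The proportion with rejection by time T is h/(h+d) × (1 - exp(-(h+d)T)).

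| Median OS | h/(h+d) | T = 1 year | T = 4 years | Ratio |
|---|---|---|---|---|
| 2 years | 0.319 | 0.319 × 0.399 = 12.7% | 0.319 × 0.870 = 27.8% | 2.2 |
| 4 years | 0.484 | 0.484 × 0.285 = 13.8% | 0.484 × 0.739 = 35.8% | 2.6 |

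Changing median OS from 2 to 4 years moves the result by 13.8 - 12.7 = 1.1 points at 1 year, and by 35.8 - 27.8 = 8.0 points at 4 years. A short horizon therefore also limits the influence of deaths.

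**2. Sensitivity to the assumed risk and hazard shape**

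| Assumed 1-year risk | Setting | 1 year | 4 years | Ratio |
|---|---|---|---|---|
| 5% | constant hazard, OS 2 / 4 years | 4.2% / 4.6% | 10.3% / 13.5% | 2.5 / 2.9 |
| 10% | constant hazard, OS 2 / 4 years | 8.5% / 9.2% | 19.5% / 25.4% | 2.3 / 2.8 |
| 20% | constant hazard, OS 2 / 4 years | 17.0% / 18.4% | 35.2% / 44.8% | 2.1 / 2.4 |
| 10% | early-loaded (Weibull shape 0.5), no deaths | 10% | 19% | 1.9 |

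Across these settings the spread is roughly 2- to 3-fold.

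**3. Denominator**

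The number of patients with a graft is unknown, and 1.3 plans no stratification by transplant history. Take 4 events, with exact (Clopper-Pearson) 95% intervals:
- All 24 treated: 4/24 = 17% (5% to 37%).
- If half have a graft (assumed): 4/12 = 33% (10% to 65%).
- If three quarters have a graft (assumed): 4/18 = 22% (6% to 48%).

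**4. Chemotherapy and RI**

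The documents give no figures from which to size either effect. The plan does not separate rejections before and after chemotherapy, and it does not ask for events to be shown by RI status.

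**The case against.** The strongest reply is that little depends on this endpoint. It is secondary and descriptive, with no test, threshold or stopping role. The hypothesis in 1.3 concerns response, less cytotoxic exposure with lower treatment-related mortality, and PFS and OS. Graft rejection is mentioned as a harm of early chemotherapy but is not among the three claims. No comparison with a historical rejection rate is planned. With 24 patients, sampling error is as large as the effect shown: the interval for 4/24, 5% to 37%, covers both the 1-year and the 4-year figures. All patients also share one follow-up schedule, so the contrast of everyone at 1 year with everyone at 4 years is an outer range. These points stand, and they make the matter minor.

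A reader might infer more than the documents support:
- **That the rate reflects these factors instead of the regimen.** It reflects them as well as the regimen. It is confounded, not uninformative.
- **That RI is imposed on everyone.** Section 3.1.2 asks only for an attempt, only under pharmacological immunosuppression, and exempts patients at excessive rejection risk.
- **That counting never ends.** Section 4.7 bounds follow-up in practice, although the endpoint is not tied to it and 4.8 gives another limit.
- **That the plan chose a flawed estimator, or declares early deaths rejection-free.** It names no estimator and says nothing on death. A plain proportion is the natural reading of 2.2.5, but it is a reading.

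Whether the endpoint is called efficacy or safety is largely preference and is not pressed here.

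What the reply does not answer is the denominator in 6.2.1.3, the missing horizon, and the absence of any rule for rejection after chemotherapy.

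**Conclusion.** The point holds as a minor one. Followed as written, the plan yields a rejection figure diluted by patients without a graft and dependent on follow-up length, early death and later chemotherapy as well as on the regimen. Where RI was attempted, it is a further contributor that a single-arm rate cannot separate from the regimen.

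For size, the same regimen would show about 2 to 2.6 times the rate at 4 years as at 1 year. This rests on the assumed constant hazard giving 15% at 1 year and on median OS of 2 to 4 years; an early-loaded hazard gives about 1.9. If half the patients have a graft, which is also assumed, the stated denominator halves the rate. The primary ORR decision is unaffected.

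**What to change.** In 2.4.6 and 6.2.1.3:
1. Restrict the analysis to patients with a graft at entry.
2. Report the cumulative incidence of new or progressive rejection at a fixed horizon, for example 12 months from first dose, with death without rejection as a competing event and an interval around the estimate. Report deaths without rejection beside it.
3. Flag events that occur after first cytotoxic chemotherapy.
4. List events after the horizon separately.
5. List each event with the patient's RI status under 3.1.2, descriptively and without a subgroup analysis.

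If every patient is followed to the horizon, this estimate equals the simple proportion among graft recipients. The gain lies in the fixed horizon, the correct denominator and a rule for patients lost before 12 months.

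The cost is a few sentences and one small analysis, with no change to treatment or enrolment. There are three downsides. Events after the horizon leave the headline figure, although they stay in the listing. The estimate rests on few patients. The Time and Events table (5.1) has no graft-assessment row and the case report forms are not in the documents, so fields for rejection date and RI status need to be confirmed.
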